10.2 Adverse Event Characteristics

- CTCAE term (AE description) and grade:** The descriptions and grading scales found in the revised NCI Common Terminology Criteria for Adverse Events (CTCAE) version

5.0 will be utilized for AE reporting. All appropriate treatment areas should have access to a copy of the CTCAE version 5.0. A copy of the CTCAE version 5.0 can be downloaded from the CTEP website

http://ctep.cancer.gov/protocolDevelopment/electronic_applications/ctc.htm.

- **For expedited reporting purposes only:**
 - AEs for the agent that are ***bold and italicized*** in the CAEPR (*i.e.*, those listed in the SPEER column, Section 10.1) should be reported through CTEP-AERS only if the grade is above the grade provided in the SPEER.
- **Attribution** of the AE:
 - Definite – The AE *is clearly related* to the study treatment.
 - Probable – The AE *is likely related* to the study treatment.
 - Possible – The AE *may be related* to the study treatment.
 - Unlikely – The AE *is doubtfully related* to the study treatment.
 - Unrelated – The AE *is clearly NOT related* to the study treatment.

10.3 Expedited Adverse Event Reporting

10.3.1 Rave-CTEP-AERS Integration

The Rave Cancer Therapy Evaluation Program Adverse Event Reporting System (CTEP-AERS) integration enables evaluation of Adverse Events (AEs) entered in Rave to determine whether they require expedited reporting and facilitates entry in CTEP-AERS for those AEs requiring expedited reporting. Sites must initiate all AEs for this study in Medidata Rave.

Treatment-emergent AEs: All AEs that occur after start of treatment are collected in Medidata Rave using the Adverse Event form, which is available for entry at each treatment course or reporting period and is used to collect AEs that start during the period or persist from the previous reporting period. AEs that occur 30 days after the last administration of the investigational study agent/intervention are collected using the Late Adverse Event form.

Prior to sending AEs through the rules evaluation process, site staff should verify the following on the Adverse Event form in Rave:

- The reporting period (course/cycle) is correct, and
- AEs are recorded and complete (no missing fields) and the form is query-free.

The CRA reports AEs in Rave at the time the Investigator learns of the event. If the CRA modifies an AE, it must be re-submitted for rules evaluation.

Upon completion of AE entry in Medidata Rave, the CRA submits the AE for rules evaluation by completing the Expedited Reporting Evaluation form (*i.e.*, checking the

NCI Protocol #: 10384

Version Date: September 5, 2023

box *Send All AEs for Evaluation* and save the form). Both NCI and protocol-specific reporting rules evaluate the AEs submitted for expedited reporting. A report is initiated in CTEP-AERS using information entered in Medidata Rave for AEs that meet reporting requirements. The CRA completes the report by accessing CTEP-AERS via a direct link on the Medidata Rave Expedited Reporting Evaluation form. Contact the CTSU Help Desk at [name] or by email at [contact] if you have any issues submitting an expedited report in CTEP-AERS.

In the rare occurrence that internet connectivity is lost, a 24-hour notification is to be made to CTEP by telephone at [contact]. Once internet connectivity is restored, the 24-hour notification that was phoned in must be entered immediately into CTEP-AERS using the direct link from Medidata Rave.

Additional information about the CTEP-AERS integration is available on the CTSU members' website:

- Study specific documents: *Protocols > Documents > Protocol Related Documents > Adverse Event Reporting*, and
- Additional resources: *Resources > CTSU Operations Information > User Guides & Help Topics*.

NCI requirements for SAE reporting are available on the CTEP website:

- NCI Guidelines for Investigators: Adverse Event Reporting Requirements is available at https://ctep.cancer.gov/protocolDevelopment/electronic_applications/docs/aeguidelines.pdf.

10.3.2 Distribution of Adverse Event Reports

CTEP-AERS is programmed for automatic electronic distribution of reports to the following individuals: Principal Investigator and Adverse Event Coordinator(s) (if applicable) of the Corresponding Organization or Lead Organization, the local treating physician, and the Reporter and Submitter. CTEP-AERS provides a copy feature for other e-mail recipients.

10.3.3 Expedited Reporting Guidelines

Use the NCI protocol number and the protocol-specific patient ID assigned during trial registration on all reports.

Note: A death on study requires both routine and expedited reporting, regardless of causality as long as the death occurred within 30 days after the last administration of the investigational agent. Attribution to treatment or other cause must be provided.

Death due to progressive disease should be reported as **Grade 5 “Disease progression”** in the

NCI Protocol #: 10384

Version Date: September 5, 2023

system organ class (SOC) "General disorders and administration site conditions." Evidence that the death was a manifestation of underlying disease (e.g., radiological changes suggesting tumor growth or progression; clinical deterioration associated with a disease process) should be submitted.

Phase 1 and Early Phase 2 Studies: Expedited Reporting Requirements for Adverse Events that Occur on Studies under an IND/IDE within 30 Days of the Last Administration of the Investigational Agent/Intervention ^{1, 2}

FDA REPORTING REQUIREMENTS FOR SERIOUS ADVERSE EVENTS (21 CFR Part 312)

NOTE: Investigators **MUST** immediately report to the sponsor (NCI) **ANY** Serious Adverse Events, whether or not they are considered related to the investigational agent(s)/intervention (21 CFR 312.64)

An adverse event is considered serious if it results in **ANY** of the following outcomes:

- 1) Death
- 2) A life-threatening adverse event
- 3) An adverse event that results in inpatient hospitalization or prolongation of existing hospitalization for ≥ 24 hours
- 4) A persistent or significant incapacity or substantial disruption of the ability to conduct normal life functions
- 5) A congenital anomaly/birth defect.
- 6) Important Medical Events (IME) that may not result in death, be life threatening, or require hospitalization may be considered serious when, based upon medical judgment, they may jeopardize the patient or subject and may require medical or surgical intervention to prevent one of the outcomes listed in this definition. (FDA, 21 CFR 312.32; ICH E2A and ICH E6).

ALL SERIOUS adverse events that meet the above criteria **MUST** be immediately reported to the NCI via electronic submission within the timeframes detailed in the table below.

Hospitalization	Grade 1 and Grade 2 Timeframes	Grade 3-5 Timeframes
Resulting in Hospitalization ≥ 24 hrs	10 Calendar Days	24-Hour 5 Calendar Days
Not resulting in Hospitalization ≥ 24 hrs	Not required	

NOTE: Protocol specific exceptions to expedited reporting of serious adverse events are found in the Specific Protocol Exceptions to Expedited Reporting (SPEER) portion of the CAEPR.

Expedited AE reporting timelines are defined as:

- o "24-Hour; 5 Calendar Days" - The AE must initially be submitted electronically within 24 hours of learning of the AE, followed by a complete expedited report within 5 calendar days of the initial 24-hour report.
- o "10 Calendar Days" - A complete expedited report on the AE must be submitted electronically within 10 calendar days of learning of the AE.

¹Serious adverse events that occur more than 30 days after the last administration of investigational agent/intervention and have an attribution of possible, probable, or definite require reporting as follows:

Expedited 24-hour notification followed by complete report within 5 calendar days for:

- All Grade 3, 4, and Grade 5 AEs

Expedited 10 calendar day reports for:

- Grade 2 AEs resulting in hospitalization or prolongation of hospitalization

²For studies using PET or SPECT IND agents, the AE reporting period is limited to 10 radioactive half-lives, rounded UP to the nearest whole day, after the agent/intervention was last administered. Footnote "1" above applies after this reporting period.

Effective Date: May 5, 2011

NCI Protocol #: 10384

Version Date: September 5, 2023

10.3.4 Additional Protocol-Specific Expedited Adverse Event Reporting Exclusions

For this protocol only, the AEs/grades listed below do not require expedited reporting via CTEP-AERS. However, they still must be reported through the routine reporting mechanism (Section 10.3):

CTCAE SOC	Adverse Event	Grades	≥24h Hospitalization ^a
Investigations	Lymphocyte count decreased	1-4	Regardless

^a Indicates that an adverse event required hospitalization for ≥24 hours or prolongation of hospitalization by ≥24 hours of a patient.

10.4 Routine Adverse Event Reporting

All Adverse Events **must** be reported in routine study data submissions. **AEs reported expeditiously through CTEP-AERS must also be reported in routine study data submissions.**

Adverse event data collection and reporting, which are required as part of every clinical trial, are done to ensure the safety of patients enrolled in the studies as well as those who will enroll in future studies using similar agents. AEs are reported in a routine manner at scheduled times during the trial using Medidata Rave. For this trial the Adverse Event CRF is used for routine AE reporting in Rave.

10.5 Pregnancy

Although not an adverse event in and of itself, pregnancy as well as its outcome must be documented via **CTEP-AERS**. In addition, the **Pregnancy Information Form** included within the NCI Guidelines for Adverse Event Reporting Requirements must be completed and submitted to CTEP. Any pregnancy occurring in a patient or patient's partner from the time of consent to 90 days after the last dose of study drug must be reported and then followed for outcome. Newborn infants should be followed until 30 days old. Please see the "NCI Guidelines for Investigators: Adverse Event Reporting Requirements for DCTD (CTEP and CIP) and DCP INDs and IDEs" (at http://ctep.cancer.gov/protocolDevelopment/adverse_effects.htm) for more details on how to report pregnancy and its outcome to CTEP.

10.6 Secondary Malignancy

A *secondary malignancy* is a cancer caused by treatment for a previous malignancy (e.g., treatment with investigational agent/intervention, radiation or chemotherapy). A secondary malignancy is not considered a metastasis of the initial neoplasm.

CTEP requires all secondary malignancies that occur following treatment with an agent under an NCI IND/IDE be reported expeditiously via CTEP-AERS. Three options are available to describe the event:

NCI Protocol #: 10384

Version Date: September 5, 2023

- Leukemia secondary to oncology chemotherapy (e.g., acute myelocytic leukemia [AML])
- Myelodysplastic syndrome (MDS)
- Treatment-related secondary malignancy

Any malignancy possibly related to cancer treatment (including AML/MDS) should also be reported via the routine reporting mechanisms outlined in each protocol.

10.7 Second Malignancy

A second malignancy is one unrelated to the treatment of a prior malignancy (and is **NOT** a metastasis from the initial malignancy). Second malignancies require **ONLY** routine AE reporting unless otherwise specified.

11. STUDY CALENDAR

Baseline evaluations are to be conducted within 1 week prior to start of protocol therapy. Scans and x-rays must be done \leq 4 weeks prior to the start of therapy. In the event that the patient's condition is deteriorating, laboratory evaluations should be repeated within 48 hours prior to initiation of the next cycle of therapy.

	Pre-Study	Priming	Cycle 1 ^m					Cycle 2 ^m					Cycle 3 ^m		Cycle 4-12 ⁿ		End of Treatment or Progression ^a
			Wk 1	Wk 1	Wk 2	Wk 3	Wk 4	Wk 1	Wk 2	Wk 3	Wk 4	Wk 1	Wk 3	Wk 1	Wk 3		
Hu5F9-G4 (magrolimab)		A	A	A	A	A	A	A	A	A	A	A	A	A	A		
Mogamulizumab			B	B	B	B	B		B			B	B	B	B		
Informed consent	X																
Demographics	X																
Medical history	X																
Concurrent meds ^b			X-----										X			X	
Physical exam	X	X	X	X	X	X	X	X	X	X	X	X	X	X		X	
Vital signs	X	X	X	X	X	X	X	X	X	X	X	X	X	X		X	
Height	X																
Weight	X	X	X				X					X		X			
Performance status ^c	X	X	X	X	X	X	X		X			X		X		X	
CBC w/diff, plt ^p	X	X ^p	X ^p	X	X	X	X	X	X	X	X	X	X	X			
Comprehensive Chemistry Panel ^d	X	X	X	X	X	X	X	X	X	X	X	X	X	X			
Pregnancy test ^e	X																
ABO/Rh type and screen, DAT ^f	X																
Antibody Screen ^g	X																
Extended RBC phenotyping including minor antigens such as CcDEe, Cw, MNSs, Kk, FyaFyb, and Jka Jkb ^{h,i}	X																
Adverse event evaluation			X-----										X			X	
mSWAT assessment/medical photography ^f		X						X					X	X ^f		X	
Imaging ^g	X												X ^g	X ^g		X ^g	
Flow Cytometry		X											X ^h	X ^h		X ^h	
FFPE biopsy tissue (optional)	X ^o																
Skin punch biopsies ^l	X			X								X				X	
Correlative blood collection ^k	X			X								X	X			X	

	Pre-Study	Prim ing	Cycle 1 ^m				Cycle 2 ^m				Cycle 3 ^m		Cycle 4-12 ⁿ		End of Treatment or Progression ^a
			Wk 1	Wk 1	Wk 2	Wk 3	Wk 4	Wk 1	Wk 2	Wk 3	Wk 4	Wk 1	Wk 3	Wk 1	Wk 3
A:	Hu5F9-G4 (magrolimab) : On Priming Week 1 only, a priming dose of 1 mg/kg Hu5F9-G4 (magrolimab) will be given. Then assigned dose on Cycle 1 Day 1, 8, 15, and 22, Cycle 2 Day 1, 8, 15 and 22, Cycle 3+ Day 1, 15. Cycles are 28 days long.														
B:	Mogamulizumab: 1mg/kg on Cycle 1 Day 1, 8, 15, and 22, Cycle 2+ Day 1, 15. Cycles are 28 days long.														
a:	Off-study evaluation. Cycle 12 (Week 48) visit may serve as end of treatment/progression visit														
b:	Starting from cycle 4, concurrent meds will be evaluated first week of every cycle														
c:	Note: Performance status evaluations are based on a 4 week cycle. At minimum, performance status should be evaluated at the beginning of every cycle.														
d:	Albumin, alkaline phosphatase, total bilirubin, bicarbonate, BUN, calcium, chloride, creatinine, glucose, potassium, total protein, SGOT [AST], SGPT [ALT], sodium.														
e:	Pregnancy test for women of childbearing potential.														
f:	Starting from Cycle 6, mSWAT assessment will be performed on the 1 st week of every 3 rd cycle (i.e. cycle 6, 9, 12, 15, etc.), and at the end of treatment or progression.														
g.	Patients without extracutaneous disease at screening (N0-2 and M0): scans will be performed at baseline and repeated to confirm global PR/CR, at suspicion of PD. Patients with extracutaneous disease at screening (N3 or Nx or M1): scans will be performed at baseline, Week 12, and then repeated at the end of every 3 cycles (i.e. cycle 6, 9, 12.), to confirm global PR/CR, at suspicion of PD. Scans at the time of progression or at the end of treatment do not need to be repeated if the most recent scan occurred within the past 28 days. End of cycle scans should be performed between Days 15 and 28, or Day 1 of the following cycle. Either PET/CT or diagnostic CT chest/abdomen/pelvis +/- neck may be used. Visit windows of \pm 7 days allowed.														
h.	Patients with B1 or B2 disease at baseline: Flow cytometry will be performed at Week 1, Week 12, and then repeated on the 1 st week of every 3 rd cycle (i.e. cycle 6, 9, 12). Flow cytometry will also be performed to confirm global PR/CR, if progression of disease is suspected and at end-of-treatment. Patients with B0 disease at baseline: Flow cytometry will be performed at baseline, to confirm a partial or complete response, if progression of disease is suspected, and at end-of-treatment.														
j.	Biopsies are not required for patients with a complete response in the skin.														
k.	Correlative blood collection will be performed at baseline, Cycle 1 Week 2, Cycle 3 Week 3, Cycle 6 Week 1, and at PD/EOT.														
l.	ABO/Rh, RBC genotyping, and DAT testing are not required for patients randomized to the mogamulizumab-only arm. This will be done prior to crossover to the combination arm if applicable.														
m.	For cycle 1 through cycle 3, visit windows of \pm 2 days allowed														
n.	Starting from cycle 4, visit windows of \pm 3 days allowed														
o.	Archival tissue sample within 6 months prior to registration														
p.	Within 24 hours prior to each of the first 2 doses of Hu5F9-G4 infusion, patients must have a documented hemoglobin level of \geq 9 g/dL. Patients who do not meet these criteria must be transfused and have their hemoglobin rechecked to meet the minimum hemoglobin threshold prior to administering each of the first 2 doses of Hu5F9-G4. An additional hemoglobin must be checked 3 to 6 hours after the initiation of the first and second doses of Hu5F9-G4. The patient should be transfused as clinically appropriate. Investigators should consider additional hemoglobin monitoring during the first week of treatment in patients with symptoms of anemia or at increased risk for complications of anemia.														
q.	RBC genotyping must be performed if a patient received any RBC or whole blood transfusion within the previous 3 months (unless laboratory has availability for special techniques for performing phenotyping for patients with recent transfusion). This may be performed for all patients in lieu of an extended RBC phenotyping.														

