6.2 Definition of Dose-Limiting Toxicity

DLT Definition: A DLT is defined as any Grade 3 or greater AE that is assessed as related to at least 1 study treatment that occurs during the DLT Assessment Period (DLT exceptions are defined below). The DLT period during the phase 1 study will be 4 weeks from the first infusion of Hu5F9-G4 (magrolimab) (priming infusion). To be assessable for a DLT, patients must have

NCI Protocol #: 10384

Version Date: September 5, 2023

received at least three infusions of Hu5F9-G4 (magrolimab), two infusions of mogamulizumab, and completed four weeks of assessment, or else have experienced a DLT anytime after receiving the priming dose of Hu5F9-G4 (magrolimab). Patients unable to receive the planned treatment during the four weeks due to treatment-related adverse events will also be considered to have experienced a DLT.

DLT Exceptions: The following are exceptions to the DLT definition and will NOT be considered a DLT:

- Grade 3 anemia; however, Grade 3 hemolytic anemia is considered a DLT.
- Grade 3 hyperbilirubinemia that resolves to \leq Grade 2 with supportive care within 1 week and is not associated with other clinically significant consequences.
- Transient Grade 3 nausea, vomiting, diarrhea, local reactions, influenza-like symptoms, myalgias, fever, headache, acute pain, or skin toxicity that resolves to \leq Grade 2 within \leq 72 hours after medical management (e.g., supportive care, including immunosuppressant treatment) has been initiated.
- Grade 3 fatigue that resolves to \leq Grade 2 within 1 week on study.
- Grade 3 magrolimab-related infusion reactions in the absence of an optimal pretreatment regimen, which is defined as acetaminophen or a comparable non-steroidal anti-inflammatory agent, plus an antihistamine and corticosteroids.
- Grade 3 electrolyte disturbances (hyperkalemia, hypophosphatemia, hyperuricemia, etc.) that resolves to \leq Grade 2 or baseline within 1 week.
- Grade 3 or 4 lymphopenia or grade 3 leukopenia not associated with other clinically significant consequences.
- Transient (\leq 48 hours) Grade 3 fatigue, local reactions, flu-like symptoms, fever, headache, nausea, emesis, and diarrhea.
- Other single laboratory values out of normal range that have no clinical correlate, and resolve to Grade \leq 1 or to baseline within 7 days with adequate medical management.
- Tumor flare phenomenon defined as local pain, irritation, or rash localized at sites of known or suspected tumor.

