7.1.2 Tumor Lysis Syndrome

In the case of evidence for tumor lysis syndrome associated with Hu5F9-G4 (magrolimab), patients will be admitted to the hospital as clinically indicated. Standard management will include vigorous IV hydration; correction of acidosis, if present; hypouricemic agents; and close monitoring of serum uric acid, phosphorus, and electrolytes. Study treatment should be held until the patient's condition resolves or stabilizes.

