Interim Safety Analysis: Before proceeding to the Phase 2 study, the Phase 1b will report satisfaction of the DLT safety criteria and provide a complete report of adverse events and a listing of patients in the Phase 1b that were taken off treatment due to adverse events, and the cycles in which that occurred. During the Phase 2 study, a formal amendment will be considered if at any point the first course DLT rate exceeds 30%, inclusive of all Phase 1b/2 patients treated at the RP2D on the combination of Hu5F9-G4 (magrolimab) and mogamulizumab, and accrual will be held pending review. Additional toxicity monitoring rules beyond cycle 1 follow:

The grade 3-4 AE rate of mogamulizumab throughout multiple cycles of the MAVORIC study was 41% (75 of 184 patients), with 28/184 stopping for AE (15%). The median PFS was approximately 7.7 months. Two of the three on-treatment deaths with mogamulizumab single agent (sepsis and polymyositis) were considered treatment related (2 of 184).

The optimistic scenario is that the combination of Hu5F9-G4 (magrolimab) and mogamulizumab will have enhanced activity over single agent mogamulizumab offsetting the potential increased toxicity of the doublet over single agent mogamulizumab ab. It is expected that the toxicity will be higher with the doublet, and this will be further amplified if the combination is active, keeping patients on treatment longer and increasing the chance of cumulative toxicities and sporadic toxicities. As a result, the rules for toxicity monitoring throughout the study will trigger a Toxicity Monitoring Committee (TMC) meeting (members of the TMC will receive the report at the time of the trigger and will respond within two weeks of the report of the trigger) to decide upon further action based on the totality of the data on both arms. The Toxicity Monitoring Committee will have the authority to hold study accrual and will send a report to the Data Coordinating Center, which will also be reviewing severe adverse events and the totality of the data at the regularly scheduled intervals (every 6 months) [separate from the monthly data coordination center review of data]. The Toxicity Monitoring Committee will consist of the NCI drug monitor, the NCI disease monitor, the study PI and the site PI/treating physician, or the respective designees for the toxicity committee members.

The triggering rules for Toxicity Monitoring Committee are as follows:

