- 1) Any treatment-related death on the combination of Hu5F9-G4 (magrolimab) and mogamulizumab (considered possibly related) will trigger a Toxicity Monitoring Committee meeting. The request for a Toxicity Monitoring Committee meeting will be made within 24 hours of the report of a treatment-related death to the Data Coordinating Center.
- 2) If the reported data documents at least 2 patients and more than 30% of patients stop therapy on the doublet due to adverse events before the third cycle, the Data Coordinating Center (which meets monthly) will trigger a Toxicity Monitoring Committee meeting. If

this rule is triggered, the Toxicity Monitoring Committee can hold accrual or permit continued accrual. If permitting continued accrual, the Toxicity Monitoring Committee will make a recommendation for continuing to monitor the off-treatment pattern after the first time this condition is triggered.

The Data Coordinating Center will compare the rate of AEs meeting DLT criteria (occurring at any point during treatment including outside of the DLT period) on both arms using an alpha-spending function approach with an O'Brien-Fleming monitoring boundary beginning at about 33% of the expected information (28 total patients). The second planned evaluation is at 56 total patients (2/3 information). The Data Coordinating Center will employ a one-sided type I error of 0.15 (spending 0.044 alpha at 28 patients and the remainder at 56 patients). A statistically significant increase in the rate of AEs on the doublet arm by these rules will result in the Data Coordinating Center calling for a Toxicity Monitoring Committee. For example, there is greater than a 70% chance of triggering this review if the cumulative rate of AEs meeting the DLT criteria in the control arm is 41% and the cumulative rate in the doublet arm is 62%. As a further example, this rule will be triggered if the cumulative rate of DLT-level AEs (over all cycles) is 5/14 vs 10/14 for the SOC vs doublet arm and will also be triggered for 11/28 (39%) vs 16/28 (57%) AEs on the respective arms. Once triggered, the Toxicity Monitoring Committee will have the same options as in item 2 above.

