10.1 Comprehensive Adverse Events and Potential Risks List(s) (CAEPRs)

10.1.1 CAEPR for CTEP IND Agent

10.1.1.1 CAEPR for Hu5F9-G4 (magrolimab)

Comprehensive Adverse Events and Potential Risks list (CAEPR) for Hu5F9-G4 (magrolimab, NSC 809249)

The Comprehensive Adverse Events and Potential Risks list (CAEPR) provides a single list of reported and/or potential adverse events (AE) associated with an agent using a uniform presentation of events by body system. In addition to the comprehensive list, a subset, the Specific Protocol Exceptions to Expedited Reporting (SPEER), appears in a separate column and is identified with bold and italicized text. This subset of AEs (SPEER) is a list of events that are protocol specific exceptions to expedited reporting to NCI (except as noted below). Refer to the 'CTEP, NCI Guidelines: Adverse Event Reporting Requirements'

NCI Protocol #: 10384

Version Date: September 5, 2023

http://ctep.cancer.gov/protocolDevelopment/electronic_applications/docs/aeguidelines.pdf for further clarification. Frequency is provided based on 579 patients. Below is the CAEPR for Hu5F9-G4 (magrolimab).

NOTE: Report AEs on the SPEER **ONLY IF** they exceed the grade noted in parentheses next to the AE in the SPEER. If this CAEPR is part of a combination protocol using multiple investigational agents and has an AE listed on different SPEERs, use the lower of the grades to determine if expedited reporting is required.

Version 2.1, May 24, 2022¹

Adverse Events with Possible Relationship to Hu5F9-G4 (Magrolimab) (CTCAE 5.0 Term) [n= 579]			Specific Protocol Exceptions to Expedited Reporting (SPEER)
Likely (>20%)	Less Likely (<=20%)	Rare but Serious (<3%)	
BLOOD AND LYMPHATIC SYSTEM DISORDERS			
Anemia			Anemia (Gr 2)
GASTROINTESTINAL DISORDERS			
	Diarrhea		Diarrhea (Gr 2)
	Nausea		Nausea (Gr 2)
	Vomiting		Vomiting (Gr 2)
GENERAL DISORDERS AND ADMINISTRATION SITE CONDITIONS			
	Chills		Chills (Gr 2)
	Fatigue		Fatigue (Gr 2)
	Fever		Fever (Gr 2)
INJURY, POISONING AND PROCEDURAL COMPLICATIONS			
Infusion related reaction			Infusion related reaction (Gr 2)
INVESTIGATIONS			
	Blood bilirubin increased		
	Platelet count decreased		
METABOLISM AND NUTRITION DISORDERS			
	Anorexia		
	Hypomagnesemia		
NERVOUS SYSTEM DISORDERS			
	Headache		Headache (Gr 2)
SKIN AND SUBCUTANEOUS TISSUE DISORDERS			
	Dry skin		
	Rash acneiform		

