	Aspartate aminotransferase increased ^{2,6}		
	Blood bilirubin increased ^{2,6}		
	GGT increased ^{2,6}		
	Lymphocyte count decreased ²		Lymphocyte count decreased ² (Gr 2)
	Neutrophil count decreased ²		Neutrophil count decreased ² (Gr 2)
	Platelet count decreased ²		Platelet count decreased ² (Gr 2)
	White blood cell decreased ²		White blood cell decreased ² (Gr 2)
METABOLISM AND NUTRITION DISORDERS			
		Tumor lysis syndrome	
MUSCULOSKELETAL AND CONNECTIVE TISSUE DISORDERS			
	Arthritis ²		
NERVOUS SYSTEM DISORDERS			
	Peripheral motor neuropathy ²		
RESPIRATORY, THORACIC AND MEDIASTINAL DISORDERS			
	Pneumonitis ²		
SKIN AND SUBCUTANEOUS TISSUE DISORDERS			
		Erythema multiforme ²	
	Rash maculo-papular ²		Rash maculo-papular ² (Gr 2)
		Skin and subcutaneous tissue disorders - Other (drug eruption, toxic skin eruption) ²	
	Skin hypopigmentation ²		
		Stevens-Johnson syndrome ²	
		Toxic epidermal necrolysis ²	

¹This table will be updated as the toxicity profile of the agent is revised. Updates will be distributed to all Principal Investigators at the time of revision. The current version can be obtained by contacting [contact]. Your name, the name of the investigator, the protocol and the agent should be included in the e-mail.

²Immune-mediated adverse reactions have been reported in patients receiving KW-0761 (mogamulizumab). Adverse events potentially related to KW-0761 (mogamulizumab) may be manifestations of immune-mediated adverse events. In clinical trials, most immune-mediated adverse reactions were reversible and managed with interruptions of KW-0761 (mogamulizumab), administration of corticosteroids and supportive care.

³Infusion reactions, including high-grade hypersensitivity reactions, anaphylaxis, and cytokine release syndrome, which have been observed following administration of KW-0761 (mogamulizumab), may manifest as fever, chills, shakes, itching, rash, hypertension or hypotension, or difficulty breathing during and immediately after administration of KW-0761 (mogamulizumab).

⁴Acute graft-versus-host disease has been observed in patients treated with KW-0761 (mogamulizumab) who subsequently received hematopoietic stem cell transplants.

⁵Infection may include any of the infection sites under the INFECTIONS AND INFESTATIONS SOC.

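### The scheduled chemistry panel omits phosphate, uric acid and magnesium, so routine draws give only a partial early signal of tumor lysis and none of hypomagnesemia

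*Combined protocol and SAP*

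**What the plan says.** Section 11, footnote d, spells out the comprehensive chemistry panel: "Albumin, alkaline phosphatase, total bilirubin, bicarbonate, BUN, calcium, chloride, creatinine, glucose, potassium, total protein, SGOT [AST], SGPT [ALT], sodium". The panel is marked before study, at priming and at the on-treatment visits.

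Three other parts of the plan refer to analytes outside that list.

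- Section 7.1.2 describes what to do when there is evidence of tumor lysis associated with magrolimab. Management then includes "close monitoring of serum uric acid, phosphorus, and electrolytes".
- Section 10.1 lists "Tumor lysis syndrome" for mogamulizumab in the rare-but-serious column (<3%), and "Hypomagnesemia" for magrolimab in the less-likely column (<=20%).
- Section 6.2 has a DLT exception for "Grade 3 electrolyte disturbances (hyperkalemia, hypophosphatemia, hyperuricemia, etc".) when the disturbance resolves within 1 week to Grade 2 or less or to baseline.

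The DLT criteria remain in use in phase 2. Under Section 9.1, accrual is held pending review, and an amendment considered, "if at any point the first course DLT rate exceeds 30" percent. The Data Coordinating Center will also "compare the rate of AEs meeting DLT criteria (occurring at any point during treatment including outside of the DLT period) on both arms", with looks at 28 and 56 patients in total.

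**The concern.** Footnote d is a closed list, so a site that follows the calendar exactly never measures phosphate, uric acid or magnesium unless something prompts it. For tumor lysis, two of the laboratory items that Section 7.1.2 wants watched are requested only after the condition is already apparent, and there is no pre-treatment value to compare them with. For magnesium, a listed possible effect of the investigational drug has no scheduled test at all.

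What is at stake is early safety detection for individual patients. A secondary question is whether the omission could reach the DLT-based monitoring rules, since the DLT exception names disturbances of two of the missing analytes.

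**Working it through.** No power, alpha or sample-size figure bears on this point. The check is a comparison of lists, followed by a count of draws.

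**1. Is the panel the only source?** Footnote d names 14 analytes. No other row or footnote in Section 11 adds phosphate, uric acid or magnesium, and the organ-function criteria in Section 3.1.5 do not require them. Section 7.1.3 mentions serum chemistries as set out in the schedule of assessments, which leads back to the same panel.

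**2. What the plan names against what it schedules.**

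| Item | Where named | In footnote d? |
|---|---|---|
| Potassium (hyperkalemia) | 6.2 exception | Yes |
| Phosphate (hypophosphatemia) | 6.2 exception | No |
| Uric acid (hyperuricemia) | 6.2 exception | No |
| Electrolytes | 7.1.2 | Yes |
| Phosphorus | 7.1.2 | No |
| Uric acid | 7.1.2 | No |
| Magnesium | 10.1.1.1 risk list | No |

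So 1 of the 3 disturbances named in the exception is scheduled, and 1 of the 3 items named for tumor lysis. Magnesium is named in neither section; its case rests on the magrolimab risk list alone. Calcium, creatinine and BUN, which also inform on tumor lysis, are scheduled.

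**3. Where the existing draws fall (combination arm, 12 cycles completed).** Set Cycle 1 Week 1 as week 0.

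- Pre-study: 1 draw
- Priming (week -1): 1
- Cycle 1 (weeks 0 to 3): 4
- Cycle 2 (weeks 4 to 7): 4
- Cycle 3 (weeks 8 and 10): 2
- Cycles 4 to 12, Week 1 only (weeks 12 to 44): 9

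Total: 1 + 1 + 4 + 4 + 2 + 9 = 21, of which 20 are on treatment. The calendar grid is misaligned in the text available. If Week 3 of Cycles 4 to 12 is also marked, the total is 21 + 9 = 30, with 29 on treatment. On either reading, none includes the three analytes.

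The draws from week -1 to week 7 number 1 + 4 + 4 = 9, and each is followed by another one week later. From Cycle 3 on, the gaps are longer than a week. The +/-2 day visit window in Cycles 1 to 3 can stretch a 7-day gap to 7 + 2 + 2 = 11 days.

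**4. What it would take to change a DLT count.** From Section 6.2, a missed disturbance of phosphate or uric acid matters only if all of these hold:

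- it is Grade 4, or Grade 3 lasting more than 1 week, because a Grade 3 change that resolves within the week is exempt;
- it is judged related to at least one study treatment;
- it is not found clinically or by unscheduled local testing;
- it is that patient's only DLT-level AE.

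**5. Are these disturbances expected drug effects?** Neither agent's list of possibly related events includes hypophosphatemia or hyperuricemia. For mogamulizumab, hypophosphatemia and hypomagnesemia appear only among events with insufficient evidence of causation (Section 10.1.2.1). Hyperuricemia appears on neither agent's lists.

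**The case against.** The strongest reply is that nothing of consequence is lost. Potassium, calcium, creatinine and BUN are drawn at baseline and weekly from priming through Cycle 2. Section 7.1.2 brings in uric acid and phosphorus when tumor lysis is evident, AE evaluation runs throughout, and nothing bars a site from ordering unscheduled tests. Section 7.1.2 is written for magrolimab-associated tumor lysis, whereas the listed risk is mogamulizumab's and sits in the <3% band. Magnesium rests on a single line of a risk list.

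Most of this stands. It shows that the gap is partial and that few events are likely to be missed. It does not show that uric acid, phosphate or magnesium are watched before a problem appears. Because the listed tumor lysis risk belongs to the drug given in both arms, it also argues for testing both.

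A reader might infer that the DLT exception cannot be applied without scheduled baseline and 1-week values. The text does not support that. Return to Grade 2 or less is sufficient by itself, so no baseline is strictly required, and a local repeat can settle resolution. Scheduled potassium draws from Cycle 3 on are likewise more than a week apart.

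A reader might also infer that DLT rates are understated or the between-arm comparison biased. The documents show neither. The panel is common to both arms. Open-label treatment could make unscheduled testing differ by arm, but nothing in the documents indicates that it does. Whether a clinically silent change can reach Grade 3 depends on CTCAE, which version "5.0 will be utilized for AE reporting" but whose thresholds the documents do not reproduce.

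**Conclusion.** The omission is confirmed from the text, and its consequence is modest. Scheduled data give no uric acid or phosphate signal of tumor lysis and no monitoring for hypomagnesemia. Because the other relevant chemistries are already drawn, this is a partial gap in safety monitoring.

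The link to the DLT rules is only a possibility. It needs every condition in step 4 of the working, and no such effect is shown. Phase 1b is complete (1 DLT in 6 patients, RP2D set), and nothing in the documents puts that decision in doubt. The remaining phase 2 rules lead to a hold for review or to a Toxicity Monitoring Committee meeting that weighs the totality of the data. ORR6 is unaffected.

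The number of events that would be missed cannot be derived, because the documents give no usable rates for these disturbances; it is probably small. The point assumes that sites follow footnote d as written and do not routinely add these tests. It is a cheap improvement of low severity.

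**What to change.** Add phosphate, uric acid and magnesium to footnote d, at baseline and at the existing chemistry draws, in both arms. At minimum, cover baseline and priming through Cycle 2 (the corresponding weeks in the control arm), when draws are weekly. Follow up abnormal values with the usual local repeat, in particular from Cycle 3 on, where the next scheduled draw is more than a week away.

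The cost is one footnote edit and three inexpensive assays on blood already drawn. No scheduled visit, procedure or staff time is added. The downside is minor assay expense, an occasional unscheduled repeat, and a few more laboratory AEs to grade and attribute.
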